Toxicity Management/ Dose Modification	Management of Dose-Limiting Toxicities  Toxicity that meets the protocol definition of DLT will be managed by either discontinuing the patient from further participation in the study, or the patient may continue on study if there is evidence of response or other clinical benefit, but must do so at a reduced dose of study drug, and ONLY following discussion with the Sponsor's Medical Monitor(s). Patients may not be retreated following the occurrence of a DLT until retreatment criteria have been met.  Exceptions to continuing on study at a reduced dose include evidence of pulmonary, neuro-ocular, nephro-, or hepatotoxicity as detailed in the protocol Criteria for Treatment Discontinuation. In such instances patients must be permanently discontinued from treatment with study drug.  Management of Other Toxicities
	Toxicity that does not meet the protocol definition of DLT, but nevertheless warrants dose modification may be managed by either dose reduction or temporary interruption of study drug in order to allow for amelioration of the toxicity.
DLT Definition	
 
Any of the following toxicities, if judged to be associated with study drug (i.e., possibly related, probably related, or related), will be considered a DLT for the purposes of this trial.
 
1. Evidence of pulmonary fibrosis, any grade (patient must be permanently discontinued)
 
2. Grade 3 non-hematologic toxicity regardless of duration with the exceptions of: 
 
Grade 3 nausea, vomiting, diarrhea, or fatigue lasting ≤ 2 days with best supportive care
 
Grade 3 asymptomatic electrolyte abnormalities lasting ≤ 3 days that are not considered clinically relevant by the Investigator and that resolve with medical therapy
 
 
 
3. AST and/or ALT elevation > 3 × ULN (or > 3 × baseline if elevated at study entry as allowed by study eligibility criteria), with total bilirubin > 2 × ULN without initial
 

	findings of cholestasis (i.e., no elevation in serum alkaline phosphatase [ALP]), that cannot be explained by other factors
	4. Any Grade 4 non-hematologic toxicity with the exception of:  • Grade 4 asymptomatic electrolyte abnormalities lasting < 7 days that are not considered clinically significant by the Investigator and that are controlled with medical therapy

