#### 6.6.2.2. Rules for Dose Escalation and Cohort Expansion in Phase 1a

Dose escalation of AVID100 is based on demonstrated tolerability during Cycle 1 (i.e., the initial 3 weeks of dosing) and the occurrence of DLTs\* thought to be associated with (i.e., possibly related, probably related, or related to) study drug. The rules for dose escalation and identification of the MTD(s)\* in this study are as follows:

\*See Section 6.8.3; Definition of DLT and Section 6.9; Definition of Maximum Tolerated Dose

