### 6.8.2 Toxicity Management and Dose Modification

If a significant toxicity thought to be related to study drug is experienced at any point during the patient's participation in the study, the Investigator will determine:

- Whether that toxicity is dose-limiting (see **Section 6.8.3**; Definition of DLT), thus requiring either dose reduction or discontinuation from study; or
- Whether the toxicity does not meet the protocol definition of DLT, but nevertheless warrants dose modification, in which case the Investigator may elect to either reduce the dose of study drug, or temporarily interrupt dosing with study drug, in order to allow for amelioration of the toxicity.

For additional information on toxicity management and dose modification, see **Section 8.1**; Determination of DLT versus Non-DLT, and **Section 8.3**; Dose Modification Options.

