#### 6.8.3 Definition of DLT

Any of the following toxicities, if judged to be associated with study drug (i.e., possibly related, probably related, or related), will be considered a DLT for the purposes of this trial.

- 1. Evidence of pulmonary fibrosis, any grade (patient must be permanently discontinued)
- 2. Grade 3 non-hematologic toxicity regardless of duration, with the exceptions of:
  - Grade 3 nausea, vomiting, diarrhea, or fatigue lasting  $\leq$  2 days with best supportive care
  - Grade 3 asymptomatic electrolyte abnormalities that are not considered clinically significant by the Investigator and that are controlled with medical therapy
- 3. AST and/or ALT elevation  $> 3 \times \text{ULN}$  (or  $> 3 \times \text{baseline}$  if elevated at study entry as allowed by study eligibility criteria; see **Section 4.3.1** #7), with total bilirubin  $> 2 \times \text{ULN}$  without initial findings of cholestasis (i.e., no elevation in serum alkaline phosphatase [ALP]), that cannot be explained by other factors
- 4. Any Grade 4 non-hematologic toxicity with the exception of:
  - Grade 4 asymptomatic electrolyte abnormalities lasting < 7 days that are not considered clinically significant by the Investigator and that are controlled with medical therapy
- 5. Neutropenia that is:
  - ≥ Grade 3 and associated with fever (ANC < 1000 per mm³; temperature > 38.3°C [101°F] or a sustained temperature of ≥ 38 °C [100.4°F] for > 1 hour ) (i.e., febrile neutropenia)
  - Grade 4 and sustained (ANC < 500 per mm^3, duration > 5 days)
- 6. Thrombocytopenia that is:
  - Grade 3 with clinically significant hemorrhage or requirement for transfusion

- Grade 4 (platelets < 25,000 per mm^3)
- 7. Inability to complete Cycle 1 at the assigned dose (i.e., receipt of < 1 full planned dose of study drug plus 3 weeks of follow-up due to  $\geq$  Grade 3 toxicity)
- 8. Treatment delays > 2 weeks from the scheduled "next dose" due to ≥ Grade 3 toxicity Other toxicities may be considered a DLT as determined by the Investigator in conjunction with the Medical Monitor.

The above criteria will be used to make individual patient determinations regarding dose reductions, interruptions, or discontinuation throughout the course of the trial, but *only those DLTs occurring during Cycle 1* will be used to make decisions regarding cohort dose escalation and tolerability.

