#### 8.1. Determination of DLT versus Non-DLT

When an AE occurs, the Investigator will also determine whether the protocol definition of a DLT is met (Section 6.8.3). If so, the patient will be either discontinued from treatment or may continue treatment if there is evidence of an OR, SD, or other clinical benefit, but must do so at a reduced dose of study drug, and ONLY following discussion with the Sponsor's Medical Monitor(s). Patients may not be retreated following the occurrence of a DLT until retreatment criteria have been met (Section 6.7.1).

Alternatively, the Investigator may determine that the toxicity does not meet the protocol definition for DLT, but nevertheless warrants dose modification, because it is:

- Not controlled by optimal supportive care, or
- Not tolerated due to symptomatology or interference with normal daily activities

For toxicity that does not meet the protocol definition of DLT, the Investigator may, as described below, elect to prolong the infusion duration (for IRRs), reduce the dose of study drug, and/or temporarily delay dosing with study drug in order to allow for amelioration of the toxicity.

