# **FORBIUS**

2. Any other DLT (see **Section 6.8.3**; Definition of DLT) considered by the Investigator to require treatment discontinuation.

Note: Patients experiencing a DLT not listed in #1 above may continue at a reduced dose if there is evidence of an OR, SD, or other clinical benefit, provided protocol stipulated retreatment criteria delineated in **Section 6.7.1** (Retreatment Guidelines) have been met, and ONLY following discussion with the Sponsor's Medical Monitor(s)).

3. Another AE not meeting the criteria for a DLT, yet considered by the Investigator to require treatment discontinuation.

Note: AEs resulting in a patient's permanent discontinuation from study treatment, regardless of seriousness or relationship to study drug, MUST be reported promptly to the Sponsor (or designee).

- 4. Documented progressive disease at any time during the study
- 5. Treatment failure not meeting the criteria for progressive disease, but considered by the Investigator to require treatment discontinuation.
- 6. Requirement for a significant surgical procedure

Note: Patients requiring a minor surgical procedure (e.g., port placement, skin abscess drainage) may continue at the Investigator's discretion following discussion with the Sponsor's Medical Monitor(s). A brief interruption in therapy may be considered.

- 7. An intercurrent illness which, in the opinion of the Investigator, would prevent completion of study-related evaluations
- 8. Significant deviation from the protocol or eligibility criteria. Such patients will be considered protocol violations and will be discontinued from treatment
- 9. Pregnancy
- 10. Noncompliance with study or follow-up procedures
- 11. Patient withdrawal of consent and election to discontinue treatment with study drug. (Patients may leave the study at any time for any reason if they wish to do so, without any consequence.)
- 12. Termination of the study by the Sponsor
- 13. Any other reason which, in the opinion of the Investigator, would justify treatment discontinuation. In such a case, the Investigator's reason for treatment discontinuation must be recorded on the appropriate page of the eCRF.

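### The synopsis and Section 6.8.3 disagree on whether an otherwise exempt Grade 3 electrolyte abnormality lasting over 3 days is a DLT, and between 3 and 7 days the synopsis reverses the grade order

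*Combined protocol and SAP*

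**What the plan says.** The synopsis (DLT Definition) and Section 6.8.3 each give a numbered DLT list.

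- **Synopsis, criterion 2.** A Grade 3 non-hematologic toxicity is a DLT, with an exception for "Grade 3 asymptomatic electrolyte abnormalities lasting ≤ 3 days that are not considered clinically relevant by the Investigator" that also resolve with medical therapy.
- **Synopsis, criterion 4.** A Grade 4 non-hematologic toxicity is a DLT, with an exception for "Grade 4 asymptomatic electrolyte abnormalities lasting < 7 days that are not considered clinically significant by the Investigator" that are also controlled with medical therapy.
- **Section 6.8.3, criterion 2.** The Grade 3 exception covers "Grade 3 asymptomatic electrolyte abnormalities that are not considered clinically significant by the Investigator and that are controlled with medical therapy". It has no day limit.
- **Section 6.8.3, criterion 4.** The Grade 4 exception is the same as in the synopsis, with the limit of under 7 days.

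Other sections point to 6.8.3. Section 6.6.2.2 (dose escalation) says "See Section 6.8.3; Definition of DLT and Section 6.9; Definition of Maximum Tolerated Dose". Section 8.1 says that when an adverse event occurs "the Investigator will also determine whether the protocol definition of a DLT is met (Section 6.8.3". Sections 6.8.2 and 9.1 (item 2) also cite it. No clause states which list governs if the two differ.

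**The concern.** A DLT definition should give one answer for one event, and a milder event should not count when a more severe one of the same kind and duration does not. The synopsis fails the second test, and the two lists together fail the first.

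The classification has consequences. Under Section 8.1, a patient with a DLT either stops treatment or continues at a reduced dose, and continuing requires evidence of benefit and discussion with the Medical Monitor. Section 8.3.3 allows no re-escalation after a reduction. Section 6.7.1 holds the next cycle while an ongoing event meets DLT criteria. Under Section 6.6.3.3, Cycle 1 DLTs in 33.3% or more of an expansion cohort trigger re-evaluation and the next lower dose for later patients. With about 6 to 12 Phase 2a centers planned (Section 4.1.1), sites working from different lists could classify the same event differently.

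**Working it through.** The plan states no figure that depends on this point, so there is none to reproduce. The check sets the two texts side by side.

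**Step 1: classification by duration.** Take a study-drug-associated electrolyte abnormality that meets every other condition for exemption in both lists, and let d be its duration in days.

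- Synopsis: Grade 3 is exempt if d ≤ 3; Grade 4 is exempt if d < 7.
- Section 6.8.3: Grade 3 is exempt for any d; Grade 4 is exempt if d < 7.

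| Duration | Synopsis, Gr 3 | Synopsis, Gr 4 | 6.8.3, Gr 3 | 6.8.3, Gr 4 |
|---|---|---|---|---|
| d ≤ 3 | not DLT | not DLT | not DLT | not DLT |
| 3 < d < 7 | **DLT** | **not DLT** | not DLT | not DLT |
| d ≥ 7 | DLT | DLT | not DLT | DLT |

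The lists agree on Grade 4 throughout. They conflict on every otherwise exempt Grade 3 event with d > 3. The grade reversal appears only in the synopsis, for 3 < d < 7.

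**Step 2: can the window occur?** Section 7.2.7 schedules Cycle 1 chemistry on Day 4 (± 1 day) and Day 8. An abnormality first seen on nominal Day 4 and still present on Day 8 has lasted about 8 − 4 = 4 days, which is inside the window.

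**Step 3: effect on the Phase 2a rule.** Planned cohort sizes are about 15 (SCCHN, Sq-NSCLC) and about 30 (mTNBC).

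- 15 patients: 4/15 = 26.7% and 5/15 = 33.3%.
- 30 patients: 9/30 = 30.0% and 10/30 = 33.3%.

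One reclassified patient can therefore cross the threshold if the cohort already stands one short of it. The same is true of any single DLT of any type, so this shows what is possible and not how likely it is.

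**Step 4: effect on the MTD.** Section 2.6 attributes the stop at 270 mg/m² to a lipase elevation and a thrombocytopenia, and reports no Cycle 1 DLT in the six patients evaluated at 220 mg/m². Neither event is an electrolyte abnormality, and Table 1 lists no related Grade 3 or 4 electrolyte event that the choice of list could reclassify.

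**Step 5: observed frequency.** In Table 1, 0 of 24 Phase 1a patients, across all doses and cycles, have a related Grade 3 or 4 electrolyte event. The only electrolyte entry is one Grade 1 hypokalemia. The visible part of the Phase 2a table (Section 2.3.2.2) has only Grade 2 and Grade 1 rows, so it cannot show whether a Grade 3 or 4 event occurred.

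**The case against.** **Which text is wrong.** A reader might infer that the synopsis is simply in error. The documents do not establish that. Cross-references to 6.8.3 show where the body definition sits, not which wording was intended. The synopsis differs in three places (the day limit, *relevant* for *significant*, *resolve* for *controlled*), which could reflect a deliberate rule. Section 6.8.3 is not perfectly maintained either: its criterion 3 cites item 7 of Section 4.3.1 for the AST/ALT entry limits, which are in item 6. The synopsis is also the stricter text, so deleting its limit should not be automatic. This objection stands. Four sections refer to 6.8.3 and its grade ordering is coherent, which makes it the likely operative list and no more than that.

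**Little follows in practice.** The Grade 4 exemption needs all its conditions together: asymptomatic, under 7 days, not clinically significant, and controlled. Both lists let the Investigator with the Medical Monitor call other toxicities a DLT, and Section 6.8.2 allows dose reduction or interruption for a non-DLT toxicity. This also stands and keeps the point minor.

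**Such events are rare.** A reader might infer this from Table 1. The exact one-sided 95% upper bound for 0/24 is 1 − 0.05^(1/24) = 11.7%, but that pools all Phase 1a doses. For the six patients evaluated at 220 mg/m², 0/6 gives 1 − 0.05^(1/6) = 39.3%. The data do not support a rate at the Phase 2a dose. Section 2.3.1.3 lists electrolyte depletion among the most frequent and severe toxicities of the approved anti-EGFR antibodies, so the rule may still be needed.

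**Conclusion.** The conflict is certain from the text, for otherwise exempt Grade 3 electrolyte events over 3 days. The grade reversal is equally certain but confined to the synopsis, for events over 3 and under 7 days. That 6.8.3 governs is an inference.

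The effect arises only where the synopsis list is applied. It reaches individual dose decisions and, for Cycle 1 events, the Phase 2a tolerability rule. A reader might also suspect that the recommended dose was set under an ambiguous definition. The documents do not support that, because the DLTs that fixed the MTD fall outside this criterion. No event rate at 220 mg/m² and no probability of a changed cohort decision is claimed. Severity: minor.

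**What to change.** The sponsor should confirm which Grade 3 limit was intended and then make the two lists identical.

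- **Default:** bring synopsis criterion 2 into line with 6.8.3. Delete the 3-day limit, replace *relevant* with *significant*, and replace *resolve* with *controlled*. Section 6.8.3 stays as it is.
- **If a Grade 3 day limit was intended:** put it in both lists, and make it no stricter than the Grade 4 limit of under 7 days.

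The default costs three wording changes in one synopsis criterion at the next amendment. Its downside is that otherwise exempt Grade 3 events over 3 days, which the synopsis now counts, would no longer be DLTs. That is why the intent should be confirmed first.

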### 2. SCIENTIFIC BACKGROUND AND RATIONALE

### 2.1. Background

### 2.1.1 Overview of the Target: EGFR

Several members of the HER-ERBB family of Type 1 receptor tyrosine kinases (RTK) (including EGFR/HER1/ERBB1, HER2/ERBB2, HER3/ERBB3, and HER4/ERBB4) have been proven to be important targets for cancer therapy (1-5). EGFR has been shown to be highly expressed or in some cases mutated in a variety of human malignancies. Activation of the EGFR pathway results in cell proliferation and inhibition of apoptosis as well as affecting angiogenesis and the metastatic process. EGFR (HER1, ERBB1) has been clinically validated as a target, with marketed products including both tyrosine kinase inhibitors and monoclonal antibodies directed to this cellular receptor shown to be effective therapy for selected human malignancies. EGFR tyrosine kinase inhibitors have been shown to be effective in the treatment of patients with malignancies including non-small cell lung carcinoma (NSCLC) and pancreatic carcinoma (PC), whereas anti-EGFR antibodies have been approved for treatment of colorectal carcinoma (CRC), squamous cell carcinoma of the head and neck (SCCHN), and squamous histology NSCLC (Sq-NSCLC) (6, 7). EGFR inhibitors (EGFRi) have been studied in a wide variety of other indications including but not limited to: ovarian cancer, renal cell cancer, hepatocellular cancer, and breast cancer. In these and other indications limited EGFRi activity was observed either as single agents or in combination with other therapies including chemotherapy, thereby precluding their being developed further.

#### 2.1.2 Overview of EGFR and Breast Cancer

The role of EGFR gene and protein expression as well as activation of EGFR and downstream signaling in patients with subtypes of breast cancer (BC) has been studied intensively but there is no current consensus on the importance of inhibiting this pathway in the treatment of patients with this malignancy. A wide variety of published studies have been performed over nearly three decades evaluating EGFR expression in BC using varied techniques to assess cell surface receptor expression and activation as well as gene amplification (8-16). EGFR expression has been detected in estrogen receptor/progesterone receptor (ER/PR) positive tumors (11) and HER2 amplified and non-amplified tumors (9). The majority of studies suggest that overexpression is most commonly observed in patients with poorly differentiated, inflammatory, basal, and/or triple-negative BC (TNBC) (8, 10-16) although some studies suggested greater expression in HER2+ tumors than in ER-positive BC or TNBC (9, 10, 15). The proportion of patients who are positive varies depending on the patient subset evaluated and the technique(s) used for assessment. Recent studies have been undertaken utilizing a validated modification of the DAKO PharmDx IHC assay to evaluate the proportion of patients with various levels of EGFR expression on several different tumor types. Based on nearly 250 triple TNBC tissue samples it has been determined that: (a) 25% of TNBC cases were either 2+ or 3+ in  $\geq$  50% of tumor cells; (b) 19% of TNBC cases were 2+ in  $\geq 50\%$  of tumor cells; (c) 13% of TNBC cases were  $2 + \text{ in } \ge 75\%$  of tumor cells and; (d) 6% of TNBC cases were  $3 + \text{ in } \ge 50\%$  of tumor cells.

EGFR signaling has been shown to play a role in the development and pathogenesis of BC (17) including aspects of bone metastases (18). The role of EGFR on the epithelial-mesenchymal transition (EMT) associated with tumor invasiveness, angiogenesis, and metastasis has also been

documented (19). In addition, hetero-dimerization of EGFR with HER2 and HER3 or with non ERBB family receptors (e.g., MET) may also have a role in either the pathogenesis of subsets of patients with BC or in their resistance to therapy (19).

Very limited activity has been observed in patients with metastatic BC treated with either anti-EGFR monoclonal antibodies (mAbs) or EGFR tyrosine kinase inhibitors (TKI) as single agents (19-23). Some evidence of increased activity of chemotherapy plus the anti-EGFR mAb cetuximab vs. chemotherapy alone has been documented in patients with TNBC but thus far no definitive evidence of efficacy has been presented for any regimen containing an EGFRi (24, 25). These data suggested a need to develop biomarkers to assess potential responses earlier or to select patients with TNBC and other subtypes of BC who may be more responsive to novel therapies (19).

Preclinical data document the potent activity of AVID100 both in vitro and in vivo in models of BC including TNBC (Section 2.3.1.1 and Investigator's Brochure). In this clinical study one expansion cohort will enroll patients with BC who have not received ado-trastuzumab emtansine (Kadcyla®) and have been prescreened for EGFR overexpression using a validated bioassay. Strong overexpression of EGFR, i.e.,  $\geq 3+$  intensity by immunohistochemistry (IHC) in  $\geq 50\%$ of tumor cells or  $\geq 2+$  intensity in  $\geq 75\%$  of tumor cells will be utilized as the provisional cut-off for patient entry into this study. Evaluation of EGFR gene expression will also be evaluated in parallel using a validated FISH assay but these results will not be used for selection of patients. The choice of cell surface expression of EGFR and the high cut-off value was based on the primary mechanism of antitumor activity of AVID100 which is dependent on the delivery of the DM1 cytotoxic payload to EGFR-expressing cells. The relatively limited activity of cetuximab, demonstration that cetuximab activity is increased by the addition of chemotherapy, and the strong data that tubulin-targeted agents (e.g. Paclitaxel, docetaxel, ixabepilone, eribulin, and DM1) are active in many patients with BC provide the rationale for testing AVID100 in patients who show a high degree of overexpression of EGFR. Patients with levels of HER2 that are below the level required for treatment with trastuzumab or ado-trastuzumab emtansine and who meet the criteria for EGFR-overexpression may be considered for enrollment.

### 2.1.3 Overview of EGFR and Squamous Cell Carcinoma of the Head and Neck

The EGFR pathway is a validated target for therapy of patients with SCCHN (26-29). Multiple studies have documented that EGFR is highly expressed in more than 90% of SCCHN tumor samples compared to normal squamous epithelium from non-malignant tissue (26-29) with the majority of specimens being graded 2+ or 3+ by IHC (29). Increased production of transforming growth factor alpha (TGF-α), an EGFR ligand, has also been documented to be increased in SCCHN samples compared to normal mucosa (29). Higher levels of EGFR expression in patients with SCCHN are associated with poor prognosis (26, 27, 29) as well as poor local control of the tumor and reduced responsiveness to cetuximab (29). *EGFR* mutant type III variant (*EGFR*vIII) mutations are present in up to 40% of patients with SCCHN and may contribute to resistance to therapy with anti-EGFR mAbs (28-30) despite documentation that cetuximab binds to, down-modulates, and ultimately inhibits signaling via this mutant receptor (31, 32). *KRAS* mutations occur in less than 5% of patients with SCCHN and their impact on prognosis or response to therapy has not been established (29)

Multiple clinical trials evaluating both anti-EGFR mAbs and EGFR-TKI have been completed over the last two decades. Relatively limited antitumor activity has been observed in patients treated with EGFR-TKI and none of these agents has been approved for treatment of SCCHN (26-28, 33-35). In contrast, activity has been observed with some anti-EGFR mAbs and cetuximab has been approved as a single agent as well as in combination with either chemotherapy or radiotherapy for the treatment of selected patients with SCCHN (33-36). In patients who recently progressed on a platinum-based chemotherapy regimen approximately 13% of recipients of cetuximab achieved a partial response (PR) with a median duration of response of 5.8 months (36, 37). Addition of cetuximab to a regimen of cisplatin or carboplatin plus 5-FU in patients with untreated recurrent or metastatic SCCHN improved OS from 7.4 months in the chemotherapy alone group to 10.1 months in the group receiving chemotherapy and cetuximab (38). Progression-free survival (PFS) was increased by 2.3 months (from 3.3 to 5.6 months) and 36% of the patients treated with cetuximab and chemotherapy experienced objective responses compared to a 20% response rate in recipients of chemotherapy alone (38).

Preliminary data have been presented or published on the clinical activity of other anti-EGFR mAbs as well as on EGFR-TKI. Activity has been observed with many of these agents (33, 34) but thus far the only agent with proven safety and efficacy is cetuximab (36-38). The single agent activity of cetuximab is limited but addition of cetuximab to chemotherapy in a P3 registration study resulted in an incremental improvement in response rate, PFS and OS. Studies of chemotherapy regimens including either paclitaxel or docetaxel plus cetuximab have shown promise (39), both of these approved taxanes have activity in the treatment of SCCHN and docetaxel is approved for this indication (40). These data provide support for treatment of patients with SCCHN with AVID100, an ADC targeting EGFR with a DM1 payload that is a more potent microtubule-targeted agent than available taxanes. AVID100 has shown greater activity that the unconjugated antibody (MAB100) in a variety of in vitro cell lines derived from patients with SCCHN (Section 2.2.1.1.1 and Investigator's Brochure). The preclinical data with AVID100, the documented single agent activity of cetuximab, and the documented role of paclitaxel and docetaxel in patients with SCCHN provides a strong rationale for the evaluation of AVID100 in this patient population.

